7.2. Subject Discontinuation/Withdrawal from the Study

- Subjects who discontinue post-randomization study drug will also withdraw from the study.
- A subject may choose to withdraw from the study at any time at her own request, or may be withdrawn at any time at the discretion of the Investigator for safety, behavioral, compliance, or administrative reasons.
- If a subject withdraws consent for disclosure of future information, the Sponsor or designee may retain and continue to use any data collected before such a withdrawal of consent.
- If a subject withdraws from the study, she may request destruction of any blood or urine samples taken and not tested, and the Investigator must document this in the site study records.
- Subjects who withdraw from the study will not be replaced (enrollment accounts for a predetermined dropout rate).
- The Week 12/Early Withdrawal assessments will be completed, if possible, when a subject withdraws or is withdrawn from the study (see Schedule of Assessments in [Section 1.3](#)).

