4.2.4.2. Analysis Visiting Window

Analysis windows will be used for eDiary, safety (vitals and labs) as well as quality of life endpoints.

All measurements including the ones from the unscheduled visits that fall within the “Visit Window” will be used in the windowing algorithm to determine the analysis visit. Relative study day will be derived based on [Section 4.3.3](#). Note that the date of the first double-blind dose is Day 1 and the day before the date of the double-blind first dose is Day -1. Thus, there is no Day 0.

For the safety assessments and quality of life endpoints, if there are multiple values for in one window, the visit closest to the nominal day will be selected for assessing endpoints at a particular visit and for by-visit displays. If the visits are equally distant from the nominal day, then the earlier visit will be selected. All values will be stored in analysis datasets.

Check that all records slotted to a post-treatment visit are greater or equal to 15 days after the last dose date. Any post-treatment visit occurring less than 15 days after the last dose date should be re-slotted to an on-treatment visit using the corresponding relative day windows constructed for that parameter.

Table 1. For eDiary, the following analysis visit window slotting will be used to determine weekly assessments:

Analysis window label	Visit Window
Screening	NA
Run-in	NA
Baseline	[-7, -1]

Analysis window label	Visit Window
Week 1	[1, 7]
Week 2	[8, 14]
Week 3	[15, 21]
Week 4	[22, 28]
Week 5	[29, 35]
Week 6	[36, 42]
Week 7	[43, 49]
Week 8	[50, 56]
Week 9	[57, 63]
Week 10	[64, 70]
Week 11	[71, 77]
Week 12	[78, 84]
Follow-Up for Early Withdrawals	>Last dose date + 14
Follow-Up for Completers	>Last dose date + 14

Note: Only calculate the upper bound of last dose date + 14 if the relative study day of the last dose date is ≥ 71 days

Table 2: Analysis Visit Window Slotting for Safety Laboratory and Vitals

Analysis window label	Nominal visit	Nominal day	Visit Window
Screening	Visit 1	NA	NA
Run-in	Visit 2	NA	NA
Baseline ¹	Visit 3	1	NA
Week 2	Visit 4	15	[2, 22]
Week 4	Visit 5	29	[23, 42]
Week 8	Visit 6	57	[43, 70]
Week 12	Visit 7	85	[71, last dose date + 14,]
Follow-Up for Early Withdrawals	NA	NA	>Last dose date + 14
Follow-Up for Completers	NA	NA	>Last dose date + 14

¹ See [section 4.3.4](#) for definition of baseline

Note: Only calculate the upper bound of last dose date + 14 if the relative study day of the last dose date is ≥ 71 days

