7.5. Vital Signs

Vital sign data including blood pressure, pulse rate and body temperature will be collected at all study visits except for the safety telephone follow-up visit. Body weight will be measured at Screening, baseline visit and Week 12 and Height will be measured at Screening only. Blood pressure and pulse will be measured in triplicate at each visit. The average of triplicates will be used for summary.

For all parameters, absolute values and change from baseline will be presented for scheduled visits using descriptive statistics for continuous variables. In addition, the maximum post-baseline, change from baseline to the maximum post-baseline, and change from baseline to the end of treatment will be summarized for each of the vital signs.

To further investigate changes in SBP/DBP/pulse rate from baseline, the following tables will be prepared:

- Counts and percent of subjects in each group with at least a 5/10/15 CFB at 3 consecutive post-baseline visits and at Week 12 will be produced for all subjects, by pre-existing hypertension category (Yes/No) and by baseline hypertension category (Yes/No). If the percentage of subjects in a subgroup is less than 25% of the total population, the subgroup in question will be not included in summary
- CFB in Maximum post-baseline (including 95% CI of Mean)

A by-subject listing, sorted by subject identifier, will be presented including all vital sign results (scheduled or unscheduled).

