14.3.3.3	Shift Table of L/N/H Classification for Hematology Laboratory Parameters from Baseline	SAF	Include max/min post-dose, by visit, last-post dose	EOS
14.3.3.4	Clinical Chemistry Laboratory Parameters	SAF	Include observed and CFB	EOS
14.3.3.5	Abnormal Classification of Clinical Chemistry Laboratory Parameters	SAF		EOS
14.3.3.6	Shift Table of L/N/H Classification for Clinical Chemistry Laboratory Parameters from Baseline	SAF		EOS
14.3.3.7	Maximum Post-baseline ALT and AST vs. Maximum Post-baseline Bilirubin	SAF		EOS
14.3.3.8	Listing of Subjects Potentially Met Hy's Law	SAF		EOS
Other Safety				
14.3.4.1	Vital Sign Parameters	SAF	Include all observed and CFB	EOS
14.3.4.2	Vital Sign Parameter Change from Baseline Shifts at 3 Consecutive Visits	SAF	SBP, DBP and PR	EOS
14.3.4.3	Vital Sign Parameter Change from Baseline Shifts at Week 12	SAF		EOS
14.3.4.4	Vital Sign Parameter Maximum Post-Baseline Change from Baseline	SAF		EOS
14.3.5.1	Physical Examination Shift from Baseline	SAF		EOS

[1] TL= Topline Results (priority delivery after DBL); EOS= End of Study

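### The 5/10/15 threshold counts of blood-pressure and pulse rises cannot include a woman whose last vital-sign reading is on or before Day 42

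*SAP*

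**What the plan says.** SAP 7.5 describes extra tables for changes in systolic pressure, diastolic pressure and pulse: "Counts and percent of subjects in each group with at least a 5/10/15 CFB at 3 consecutive post-baseline visits and at Week 12". The list of output tables in SAP 11.1.1 splits this into Table 14.3.4.2, "Vital Sign Parameter Change from Baseline Shifts at 3 Consecutive Visits", and Table 14.3.4.3, "Vital Sign Parameter Change from Baseline Shifts at Week 12". The two conditions are therefore two separate displays, not one joint requirement. Table 14.3.4.4, "Vital Sign Parameter Maximum Post-Baseline Change from Baseline", has no visit condition, but SAP 7.5 describes it as a mean with a 95% CI.

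SAP 4.2.4.2 assigns readings to analysis visits by study day in the table titled "Analysis Visit Window Slotting for Safety Laboratory and Vitals": Week 2 is Days 2 to 22, Week 4 is Days 23 to 42, Week 8 is Days 43 to 70, and Week 12 is "71, last dose date + 14". When a window holds several readings, "the visit closest to the nominal day will be selected for assessing endpoints at a particular visit and for by-visit displays".

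Protocol 7.2 adds: "Subjects who discontinue post-randomization study drug will also withdraw from the study". An early-withdrawal visit with vital signs is to be done if possible. No scheduled vital-sign measurement follows it.

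**The concern.** Vital signs are a secondary safety endpoint and hypertension is a named adverse event of special interest. The threshold tables are where a reader would look for how many women in each arm had a measured rise of a given size. Both tables need the woman to stay in the study: long enough for three analysis visits in a row, or to Day 71 or later for a Week 12 value. Adverse events are a listed reason for stopping drug (Protocol 7.1), and stopping drug ends follow-up. A woman who stops because of a rise can therefore lose the visits she would need in order to be counted. If the drug raises pressure or pulse and some women leave early for that reason, the loss falls more on the vibegron arm, and the counts are biased towards no difference.

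**Working it through.** **Possible runs.** The schedule has four post-baseline vital-sign visits: Weeks 2, 4, 8 and 12. Three consecutive visits can only be 2-4-8 or 4-8-12. Both runs contain Week 4 and Week 8, so missing either visit breaks both. SAP 8 expects missed visits because of COVID-19.

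**Windows filled, by day of last reading.** Scheduled visits are taken at the nominal day ± 4, plus an early-withdrawal visit, slotted by study day with one value per window.

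| Last reading | Windows filled, at most | Case in 14.3.4.2? | Case in 14.3.4.3? |
|---|---|---|---|
| Day 2 to 22 | Week 2 | no | no |
| Day 23 to 42 | Weeks 2, 4 | no | no |
| Day 43 to 70 | Weeks 2, 4, 8 | only through 2-4-8 | no |
| Day 71 or later | Weeks 2, 4, 8, 12 | either run | yes |

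An example: Week 4 visit on Day 29, early-withdrawal visit on Day 40. Both readings fall in Days 23 to 42. The Day 29 reading is kept because it is nearest the nominal day, and the exit reading is not used.

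**The boundary is the last reading, not the last dose.** Readings up to 14 days after the last dose are slotted as on treatment. With a last dose on Day 29 and an early-withdrawal visit on Day 43 (29 + 14 = 43), the visit goes to Week 8 and three windows are filled. With a last dose on Day 28 the limit is Day 42, and the Day 43 visit becomes follow-up.

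**Denominator.** SAP 7.5 gives none. The general rule in SAP 4.2.2 is subjects with available data, which removes early leavers from the Week 12 percentage. If all subjects in the Safety Analysis Set are used instead, early leavers are scored as having no rise. For the three-visit table it is unclear what available data would mean.

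**Number of women.** The sample-size text assumes 10% discontinue before Week 12 and does not say when.

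- Total: 0.10 × 200 = 20, or about 10 per arm.
- Range by Day 42: 0 to about 10 per arm.
- Even dropout over 84 days (assumed), by Day 42: 10 × 42/84 = 5 per arm, cases in neither table.
- Same assumption, by Day 70: 10 × 70/84 = 8.3 per arm with no Week 12 value. Of these, 8.3 − 5 = 3.3 can be cases only through 2-4-8.

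These figures take the day of leaving as the day of the last reading.

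**The case against.** A reader might infer that a woman who leaves early because of a rise is never counted anywhere. The documents do not support that. If she stops for an adverse event, she is counted by arm among events leading to discontinuation (Table 14.3.2.11). If the event is coded as hypertension, she is also counted among the events of special interest and in the hypertension tables (14.3.2.12, 14.3.2.15 and 14.3.2.16). Her readings enter the maximum and end-of-treatment summaries, and every result is listed. SAP 7.5 presents the threshold tables as further investigation, not as the main display.

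All of that stands, but none of it is a threshold count of measured rises. The continuous summaries dilute a few large changes: as an illustration, 3 women in 100 with an extra rise of 15 move the arm mean by 3 × 15/100 = 0.45. Adverse-event counts depend on the investigator reporting an event. The preferred-term list in SAP 5.2, reused for the hypertension tables, has no term for increased blood pressure, and pulse has no special-interest category. The protocol's definition of hypertension as an event of special interest is redacted, so its overlap with these thresholds cannot be checked.

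Two further points have force. First, SAP 7.5 does not say that visits means analysis windows. On calendar visits, Week 2, Week 4 and an early-withdrawal visit by Day 42 make three; on attended visits, a missed Week 4 need not break a run. The window reading is the better supported, because SAP 4.2.4.2 applies windows to vital signs and keeps one value per window, but the text should say so. Second, any-visit counts are noisy. Assume no drug effect, normal changes with an SD of 8 to 12 and an equal between-visit correlation of 0.4 to 0.6. Then the chance of at least one rise of t or more in four visits is 1 − E[Φ((t/SD − √ρ·Z)/√(1 − ρ))⁴], with Z standard normal. This gives 51% to 67% for t = 5 and 9% to 29% for t = 15. The SD and correlation are assumptions; the documents give neither. This is why the any-visit row should be secondary.

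**Conclusion.** The concern holds for the two threshold tables and no further. With visits read as analysis windows, a woman whose last reading is on or before Day 42 cannot be a case in either table, and one whose last reading is on Days 43 to 70 has a single route in. The number affected is not in the documents: 0 to about 10 per arm under the planned dropout, about 5 per arm if dropout is even.

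A reader might also infer that the comparison between arms is shown to be biased. It is not. Bias towards no difference needs the drug both to raise pressure or pulse and to cause early exits. The protocol reports no clinically relevant differences from placebo in heart rate or blood pressure in overactive bladder at 50 and 100 mg (Protocol 4.3). The weakness is that these counts could not show such an effect among women who leave early. It is worth correcting because the correction is cheap, but it does not undermine the safety analysis as a whole.

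**What to change.** In SAP 7.5 and Tables 14.3.4.2 and 14.3.4.3, by arm on the Safety Analysis Set:

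1. Add the count and percent with a rise of at least 5/10/15 at the last on-treatment assessment, including early-withdrawal visits.
2. As a secondary row, add the same at any on-treatment post-baseline assessment, including unscheduled visits.
3. Keep the sustained row, state that consecutive visits means analysis visits, and show its denominator as subjects with at least three analysis visits in a row.
4. State the denominator for every other row, including Week 12.

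No new data are needed. The SAP already derives maximum and end-of-treatment values for vital signs, brings unscheduled readings into any-time and maximum summaries (SAP 4.2.2), and plans laboratory shifts to the maximum, minimum and last value with a stated denominator (SAP 7.4). The cost is two extra rows per parameter and threshold. The downside is that any-visit counts include transient rises in both arms and grow with the number of visits, so completers score higher. They should be read beside the sustained and last-assessment rows.

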7.6. ECG

12-Lead ECG data will be collected at the screening visit only. All data collected will be listed.

7.7. Physical Examination

Brief physical examination data will be collected at Screening, Baseline, Week 12. Shift tables (normal, abnormal, not done) of baseline versus the last observation post-baseline [normal, abnormal (same as baseline), abnormal (new or aggravated), not done] may be generated, presenting the assessment for each component of the physical examination separately. Listing of abnormal results will be produced.

8. COVID-19 CONSIDERATIONS

This study was conducted during the COVID-19 global pandemic. During the time period of the pandemic, it is anticipated that changes in study visit schedules, missed visits, or subject discontinuations may lead to missing information (e.g., for protocol-specified procedures). In accordance with the FDA Guidance on Conduct of Clinical Trials of Medical Products during COVID-19 Public Health Emergency, it is important to capture *specific* information in the case report form that explains the basis of the missing data, including the relationship to COVID-19 for missing protocol-specified information (e.g., from missed study visits or study discontinuations due to COVID-19).

The proportion of subjects with COVID-19 impact on visits will be summarized by treatment group overall and by visit for the FAS, FAS-D and FAS-M populations. The type of impact (e.g., visit cancelled, visit postponed, etc.) and the reason (e.g. subject acquired COVID-19, Subject unable to travel due to COVID-19, investigative site closure due to COVID-19, etc.) will also be summarized. A listing based on all subjects who had COVID-19 information collected will be generated which will document the visit impacted, type of impact, reason, date of contact of any telephone visits (if applicable), and if any doses were missed due to IP

unavailability. Protocol deviations associated with COVID-19, identified with a “#COVID” in the protocol description, will also be included in the listing.

9. CHANGE FROM ANALYSIS PLANNED IN PROTOCOL

In [Section 1.1.3](#), the other efficacy endpoint of the “Change from baseline to Weeks 2, 4, 8, and 12 in average weekly number of days of abdominal pain within 1 hour of eating for all IBS subjects including IBS-D and IBS-M subjects” was changed to “Change from baseline to weeks 2,4,8, and 12 in pain within 1 hour of eating for all IBS subjects including IBS-D and IBS-M subjects” since the data was collected as Yes or No to the following question, “In the past 7 days, did you experience abdominal pain within 1 hour of eating”. The data will be summarized by visit as the proportion of subjects who improved vs not improved (no change, worsened, or missing post-baseline assessment).

Similarly, in [Section 1.1.3](#), the “Change from baseline to weeks 2, 4, 8 and 12 in the weekly number of days with pain associated with a bowel movement” was changed to “Change from baseline to weeks 2, 4, 8 and 12 in pain associated with a bowel movement”.

The following additional exploratory analyses will be conducted (See [Section 4.3.1.11](#)):

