10.8.4. Additional Questions on Abdominal Pain

1. Did you experience abdominal pain within 1 hour of eating? Yes/No
2. Did you experience abdominal pain associated with a bowel movement? Yes/No

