1.2.2. Randomization and Blinding

Randomization will occur centrally using an interactive voice or web response system (IxRS) using central, stratified block randomization. Randomization will be stratified based on the following stratification factors:

- Baseline abdominal pain intensity score (<6 vs ≥ 6) on a 0 to 10 numeric rating scale [NRS], and
- IBS subtype (IBS-D vs IBS-M)

For this study a double-blind/masking technique will be used: vibegron and its matching placebo will be packaged identically so that treatment blind/masking is maintained. The subject, the Investigator, and Sponsor personnel or delegate(s) who are involved in the treatment or clinical evaluation of the subjects will not be aware of the treatment group assignments.

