4.2.2. Reporting Conventions

General rules

In general, all collected safety data and any derived efficacy parameters from daily evening pain diary and daily bowel movement diary and PRO data will be presented in subject data listings, for all enrolled subjects. Listings will be ordered by treatment subject number, and assessment week or event date. The treatment group presented in listings will be based on the planned assignment, unless otherwise noted.

Summary tables will be provided for all randomized subjects. All demographic and baseline data will be presented by treatment arm and overall, unless otherwise specified. Efficacy, PRO and safety data will be presented by treatment arm only. In general, continuous variables will be summarized to include the population sample size (N), number of subjects with available data (n), arithmetic mean, SD, median, minimum, Q1, Q3 and maximum values. Categorical variables will be summarized by the population size (N), number of subjects with available data (n), number of subjects in each category, and the percentage of subjects in each category. Unless otherwise noted, the denominator to determine the percentage of subjects in each category will be based on the number of subjects with available data (n) in the analysis set of interest. Selective ordinal data may be summarized using both descriptive statistics and counts and percentages of subjects in each category, as appropriate.

The data analyses will be conducted using the SAS® System (SAS Institute Inc., Cary, NC) version 9.4 or above. The [REDACTED]’ standard operating procedures will be followed for the validation of all SAS programs and outputs.

Formats

Numeric data will be reported at the precision collected on the eCRF. The reported precision from non eCRF sources may be adjusted to a clinically interpretable number or decimal places.

Unscheduled Visits

Unscheduled visits will be assigned to a study visit using the all-inclusive windows defined in [Section 4.2.4](#). However, for by visit summaries, only the planned assessment time points will be summarized. Assessments at unscheduled visits will be included for “any time On-treatment” timepoints and in data listings, as well as algorithms to determine the maximum.

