4.3.1.3. Change from Baseline in API score

All endpoints will be derived at Baseline, Weeks 2, 4, 8 and 12.

- Weekly average of WAP score:
Derivation is defined as described in the first step in [Section 4.3.1.1](#).
- Weekly average number of pain-free days

[figure not shown]
Weekly average number of pain-free days is defined as the sum of all pain-free days in the past 7 days immediately prior to baseline visit (Day 1) or each of post-baseline Weeks (Weeks 2, 4, 8, 12), divided by the number of days with non-missing pain diary entries and then multiply 7. Weekly average will be set missing if more than 2 missed diary days over the past 7 days.

[figure not shown]
- Change from baseline in abdominal pain within 1 hour of eating

[figure not shown]
Change from baseline will be summarized categorically as “Improved (Yes to No)” vs “Not Improved”, where “Not Improved” is further categorized as “No Change”, “Worsened (No to Yes)”, or “Missing Post-baseline Assessment”.

- Change from baseline in abdominal pain associated with a bowel movement:

[figure not shown]
Change from baseline will be summarized categorically as “Improved (Yes to No)” vs “Not Improved”, where “Not Improved” is further categorized as “No Change”, “Worsened (No to Yes)”, or “Missing Post-baseline Assessment”.

[figure not shown]

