5.3. Other Baseline Characteristics

The data from the Daily Evening Pain Diary and Bowel Movement diary during run-in period (reviewed at Visit 3 Baseline visit) prior to first double-blind dose will be used as baseline for each subject. This includes endpoints:

- Weekly average of worst daily pain score,
- Weekly average number of pain-free days
- Daily average bowel urgency episodes,
- Weekly average number of days with bowel urgency,
- Abdominal pain within 1 hour of eating (Yes vs No),
- Abdominal pain associated with a bowel movement, (Yes vs No)
- Weekly average number of days with recurrent bowel movement,
- Daily average number of bowel movements,
- Weekly average number of days with diarrhea (Bristol Type 6 or 7),
- Weekly number of days with diarrhea (Bristol Type 6 or 7)
- Weekly average number of days with at least 1 stool with Bristol Type 3, 4, or 5 consistency
- Weekly average number of stools with Bristol Type 3, 4, or 5 consistency

In addition, the following parameters will be presented in the baseline table

- Daily average stool consistency
- Daily average number of diarrhea bowel movement
- Daily average number of stools with Bristol Type 3, 4, 5 consistency
- Weekly average number of days with constipation (Bristol Type 1 or 2)
- Daily average number of stools with constipation (Bristol Type 1 or 2)
- Weekly average number of stools with constipation (Bristol Type 1 or 2)

These will be summarized by IBS subtype (IBS-D, IBS-M) and for all IBS subjects, and treatment group using descriptive statistics for continuous data for all subjects in each analysis set.

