14.2.2.6	Shift Table of Global Improvement Scale from Baseline – IBS-M Subjects	FAS-M	Include all Weeks but Week 12 in the front	EOS
14.2.2.7	Shift Table of Global Improvement Scale from Baseline – IBS-M Subjects	FAS	Include all Weeks but Week 12 in the front	EOS
14.2.3.1 – 14.2.3.3	Change from Baseline in Weekly Average Worst Abdominal Pain Score (MMRM) – IBS-D/IBS-M/All Subjects	FAS-D/FAS-M/FAS	Include all Weeks but Week 12 in the front	TL, EOS
14.2.3.4	Change from Baseline in Weekly Average Worst Abdominal Pain Score	FAS	Place IBS-D, IBS-M and All IBS on the column and treatment arm underneath IBS columns	EOS
14.2.4.1 – 14.2.4.3	Change from Baseline in Weekly Average of Number of Pain Free Day (MMRM) – IBS-D/IBS-M/All Subjects	FAS-D/FAS-M/FAS	Include all Weeks but Week 12 in the front	EOS

Title		Analysis Set	Programming Note	Deliverable
14.2.4.4	Change from Baseline in Weekly Average of Number of Pain Free Day		Table 14.2.3.4	EOS
14.2.5.1 – 14.2.5.3	Change from Baseline in Abdominal Pain Within 1 Hour of Eating – IBS-D/IBS-M/All Subjects	FAS-D/FAS-M/FAS	Include all Weeks but Week 12 in the front	EOS
14.2.5.4	Change from Baseline in Abdominal Pain Within 1 Hour of Eating	FAS	Table 14.2.3.4 but showing proportion of subjects Improved vs Not Improved (No Change, Worsened, Missing Post-baseline Assessment)	EOS
14.2.6.1 – 14.2.6.3	Change from Baseline in Abdominal Pain Associated with a Bowel Movement – IBS-D/IBS-M/All Subjects	FAS-D/FAS-M/FAS	Include all Weeks but Week 12 in the front	EOS
14.2.6.4	Change from Baseline in Abdominal Pain Associated with a Bowel Movement	FAS	Table 14.2.3.4 but showing proportion of subjects Improved vs Not Improved (No Change, Worsened, Missing Post-baseline Assessment)	EOS
14.2.7.1 – 14.2.7.3		FAS-D/FAS-M/FAS	Include all Weeks but Week 12 in the front	EOS
14.2.7.4		FAS	Table 14.2.3.4; Include all Weeks but Week 12 in the front	EOS
14.2.8.1 – 14.2.8.3		FAS-D/FAS-M/FAS	Include all Weeks but Week 12 in the front	EOS
14.2.8.4		FAS	Table 14.2.3.4; Include all Weeks but Week 12 in the front	EOS
14.2.9.1 – 14.2.9.3		FAS-D/FAS-M/FAS	Include all Weeks but Week 12 in the front	EOS
14.2.9.4		FAS	Table 14.2.3.4; Include all Weeks but Week 12 in the front	EOS

Title		Analysis Set	Programming Note	Deliverable
14.2.10.1 – 14.2.10.3		FAS-D/FAS-M/FAS	Include all Weeks but Week 12 in the front	EOS
14.2.10.4		FAS	Table 14.2.3.4; Include all Weeks but Week 12 in the front	EOS

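### The two yes/no pain summaries count women without the symptom at baseline as not improved, which dilutes the risk difference and odds ratio; a denominator change is a cheap improvement

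*SAP*

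**What the plan says.** The protocol asks two yes/no questions at Baseline and Weeks 2, 4, 8 and 12. The first is "Did you experience abdominal pain within 1 hour of eating? Yes/No" (Protocol 10.8.4); the second concerns pain with a bowel movement.

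SAP 4.3.1.3 gives the same rule for both: "Change from baseline will be summarized categorically as “Improved (Yes to No)” vs “Not Improved". Not Improved is then divided into No Change, Worsened (No to Yes) and a missing post-baseline answer. SAP 9 repeats the rule for the eating question ("The data will be summarized by visit as the proportion of subjects who improved vs not improved (no change, worsened, or missing post-baseline assessment") and treats the bowel-movement question similarly. The notes to Tables 14.2.5.4 and 14.2.6.4 also repeat it: "showing proportion of subjects Improved vs Not Improved (No Change, Worsened, Missing Post-baseline Assessment").

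The eating endpoint is defined as change "in pain within 1 hour of eating for all IBS subjects including IBS-D and IBS-M subjects". Unless otherwise noted, percentages "will be based on the number of subjects with available data (n) in the analysis set of interest" (SAP 4.2.2). No visible text limits the denominator to women with the symptom at baseline.

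SAP 5.3 lists both answers as baseline characteristics, for example "Abdominal pain within 1 hour of eating (Yes vs No"), so some No answers at baseline are expected. Randomisation is stratified by IBS subtype and by "Baseline abdominal pain intensity score (<6 vs ≥ 6) on a 0 to 10 numeric rating scale" (SAP 1.2.2), not by either symptom.

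**The concern.** Under this rule a woman with No at baseline can only fall under No Change, Worsened or Missing. She enters the denominator as a failure whatever the treatment does. Within No Change, a woman who never had the symptom (No-No) cannot be told apart from one whose symptom persisted (Yes-Yes), although these are opposite states.

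The proportion improved therefore mixes two things: how common the symptom was at baseline, and how often it resolved. Only the second is about treatment. At stake is how easily these two endpoints can be read. A low proportion improved could mean little resolution or few women with the symptom, and part of an arm difference could come from a chance difference in baseline frequency.

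**Working it through.** **Notation.** Let q be the share with Yes at baseline and r the probability of moving to No given Yes at baseline. The all-subject proportion improved is q × r.

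**Inputs.** The documents give neither q nor r for these questions. Assumed: q = 90%, 70% and 50%; r = 50% on vibegron and 35% on placebo (a 15-point true difference). Arm sizes come from Protocol 9.2: 100 per arm randomised (all IBS) and about 50 per arm with IBS-D. Evaluable numbers are 90 per arm (SAP 1.2.1) and 45 per arm (Protocol 9.2).

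**Step 1: dilution at equal q.** Difference = q × (r1 − r0); risk ratio = r1/r0, because q cancels.

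| q | Vibegron | Placebo | Difference | Risk ratio | Odds ratio |
|---|---|---|---|---|---|
| 100% | 50.0% | 35.0% | 15.0 | 1.43 | 1.86 |
| 90% | 45.0% | 31.5% | 13.5 | 1.43 | 1.78 |
| 70% | 35.0% | 24.5% | 10.5 | 1.43 | 1.66 |
| 50% | 25.0% | 17.5% | 7.5 | 1.43 | 1.57 |

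The difference and the odds ratio shrink; the risk ratio does not.

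**Step 2: chance imbalance in q.** With no drug effect and the same r in both arms, a gap in q produces a difference of r × gap. The SD of the gap is sqrt(2q(1 − q)/n). At r = 50%:

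- n = 100 per arm, q = 90%: sqrt(2 × 0.9 × 0.1/100) = 4.2 points; × 0.5 = 2.1 points.
- n = 100 per arm, q = 70%: sqrt(2 × 0.7 × 0.3/100) = 6.5 points; × 0.5 = 3.2 points.
- n = 50 per arm (IBS-D only), q = 70%: sqrt(2 × 0.7 × 0.3/50) = 9.2 points; × 0.5 = 4.6 points.

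The expected gap under randomisation is zero, so this is added variability around the right value.

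**Step 3: does a smaller denominator cost power?** The plan gives no power figure for these questions. Its only one is for the primary endpoint: about 60% with 45 per arm, 51% vs 31%, two-sided alpha 0.10. The usual normal approximation (pooled variance under the null, unpooled under the alternative) reproduces it:

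(0.20 − 1.645 × sqrt(2 × 0.41 × 0.59/45)) / sqrt((0.51 × 0.49 + 0.31 × 0.69)/45) = 0.0294/0.1015 = 0.29, which gives 61.4%.

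Borrowing 51% vs 31% as resolution rates, with 90 evaluable per arm before restriction:

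| q | Baseline-Yes women only | All women |
|---|---|---|
| 90% | 83.2% (81 per arm) | 80.9% |
| 70% | 74.2% (63 per arm) | 66.9% |
| 50% | 61.4% (45 per arm) | 50.7% |

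Under these assumptions restriction gains power, because the women it removes carry no information on resolution.

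**The case against.** The best reply is that the planned outputs nearly contain the answer. SAP 5.3 summarises both baseline answers by subtype and treatment group, and IBS baseline tables are planned for FAS, FAS-D and FAS-M (Tables 14.1.3.5 to 14.1.3.7). SAP 4.3.1.3 keeps Improved and Worsened as separate counts. Improved divided by baseline Yes, and Worsened divided by baseline No, are the two quantities wanted, and Listing 16.2.2.4 holds the individual answers. This stands in part: a careful reader could back-calculate the ratios, provided the baseline tables show these items for the same set. But the plan does not include the ratios.

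Parts of the text are also hidden. SAP 6.3 is redacted, layouts sit in a separate programming document (SAP 11.2), and the only visible note for Tables 14.2.5.1–3 and 14.2.6.1–3 concerns the order of weeks. A restriction could exist there. What is visible is consistent and contains none.

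Baseline frequency may also be high. All women have pain-related IBS with a baseline weekly average of at least 3.0, and pain related to defecation is one of the three Rome IV features, of which two are required (Protocol 5.1). Dilution is therefore probably smaller for the bowel-movement question. Pain after eating is not an entry criterion.

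Three stronger readings are tempting, and the documents do not support them:

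- A reader might infer that the comparison is biased between arms. It is not. Under randomisation the imbalance averages to zero, and a proportion over the full analysis set is a legitimate summary.
- A reader might infer that every effect measure is diluted. The expected risk ratio is not.
- A reader might take 4.6 points as the typical shift for the stated endpoint. That figure belongs to IBS-D alone; the eating endpoint is defined for all IBS subjects, where the matching value is 3.2.

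**Conclusion.** The point holds as an improvement to reporting, not as the correction of an error that invalidates a result. On the visible text, women who cannot improve are counted as not improved, and No Change pools No-No with Yes-Yes.

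The size depends on baseline frequency, which the documents do not give. If at least 90% have the symptom, a 15-point difference loses 1.5 points or less; at 50% it is halved. At 50% resolution, one SD of chance imbalance shifts the difference by about 2 to 3 points for all IBS with 100 per arm (frequency 90% to 70%).

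Confidence is high in the mechanism and moderate in its practical effect, because of the redacted section and the unknown frequencies. A reader might infer that the efficacy conclusion is at risk. It is not: these belong to the exploratory endpoints, SAP 4.1.2 treats all efficacy analyses as descriptive, and no primary or secondary result changes.

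**What to change.** In SAP 4.3.1.3, SAP 9 and Tables 14.2.5.x and 14.2.6.x:

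- Report Yes-to-No as a proportion of women with Yes at baseline, with a missing post-baseline answer still counted as not improved.
- Report No-to-Yes as a proportion of women with No at baseline.
- Show both denominators by arm at each visit.
- Keep the all-subject proportion alongside if wanted, with No Change split into Yes-Yes and No-No.

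If the redacted SAP 6.3 or the table layouts already do this, a cross-reference in SAP 4.3.1.3 is enough. The change should be made before unblinding so that the choice of denominator cannot look data-driven.

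The cost is a few lines of SAP wording and slightly more table work, with no new data. The downside is smaller denominators, most noticeably in FAS-D and FAS-M and among women with No at baseline if the symptom is common.
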